3.0 Aims and Hypotheses

3.1 Study Aims:

- **Feasibility Aim:** To assess the feasibility of a cluster-randomized, multiple-crossover trial comparing volume control, pressure control, and adaptive pressure control modes.
- **Clinical Aim:** To evaluate the effect of the same ventilator mode intervention on days alive and free of invasive mechanical ventilation in the same population of mechanically ventilated critically ill patients.

3.2 Hypotheses:

- **Feasibility Hypothesis:** Comparing volume control, pressure control, and adaptive pressure control ventilation among mechanically ventilated ICU patients will be feasible.
- **Clinical Hypothesis:** Use of an adaptive pressure control mode for mechanically ventilated ICU patients will result in more days alive and free of invasive mechanical ventilation than use of either a volume control or pressure control mode.

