Feedback on Ventilator Mode Adherence: During the study, study personnel will monitor compliance with the assigned ventilator mode. Study personnel will remotely monitor ventilator modes up to four times daily from 4AM through 10PM Monday through Friday and during a convenience sample of weekend hours to provide feedback to treating clinicians and explore reasons why patients are not receiving the assigned mode of mechanical ventilation,

Study personnel will attend respiratory therapy group meetings, nursing unit board meetings, and ICU physician leadership meetings to educate staff about the study, solicit safety concerns and adverse events, and identify and address barriers to ventilator mode assignment compliance. This approach to daily monitoring and intermittent feedback to clinical personnel successfully achieved 80% compliance with the assigned intervention in a prior cluster-crossover trial of ventilator settings in the same ICU.³⁹

7.4 Blinding:

Similar to prior ventilator mode studies among critically ill adults, patients and clinicians will not be blinded to study group assignment.^{21,58,59} Observer bias will be minimized by use of objective endpoints collected and automated data extraction from the EHR (see *Data Collection* below).

7.5 Data Collection:

The MODE trial will primarily use structured data collected in routine clinical care, exported daily from the institution's EHR into an Enterprise Data Warehouse, along with data from the patient registration, billing, and laboratory clinical information systems. We have previously validated the quality of this method of data collection against the reference standard of two-physician manual chart review,⁶⁰ and the planned approach to electronic dataset generation for the MODE trial has already been successfully employed for the conduct of four prior pragmatic trials.^{39,61–63}

Electronically extracted data elements will include:

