7.6 Outcome Measures:**Primary Outcome:**

The primary outcome is ventilator-free days (VFDs) to day 28 after enrollment.

VFDs will be defined as the number of calendar days alive and free of invasive mechanical ventilation from the final receipt of invasive mechanical ventilation through 28 days after enrollment. Outcome ascertainment will cease at the time of hospital discharge or 28 days after enrollment, whichever occurs first. Receipt of invasive mechanical ventilation will be considered to end when patients undergo the final tracheal extubation or disconnection of the ventilator from a tracheostomy tube between enrollment (day 1) and day 28 after enrollment. Patients who die prior to discharge on or before day 28 will receive zero VFDs. Patients whose final receipt of invasive mechanical ventilation occurs on the day of enrollment and survive to day 28 will receive 27 VFDs. Patients who continue to receive invasive mechanical ventilation at day 28 will receive zero VFDs. Patients who are discharged from the hospital prior to day 28 and are receiving invasive mechanical ventilation at the time of discharge will receive zero VFDs. Patients who are removed from invasive mechanical ventilation and are discharged from the hospital without invasive mechanical ventilation prior to 28 days will be assumed to remain alive and

free of invasive mechanical ventilation between hospital discharge and day 28. For patients who are removed from invasive mechanical ventilation, return to invasive mechanical ventilation, and are subsequently removed again from invasive mechanical ventilation prior to day 28, VFDs will be counted from the final receipt of invasive mechanical ventilation prior to day 28.

Feasibility Outcomes

- Exposure to assigned study mode in first 3 days: proportion of time in the assigned mode while receiving invasive mechanical ventilation in the study ICU between enrollment and 72 hours after enrollment.
- Adherence to study mode in first 3 days: proportion of time in the assigned mode while receiving invasive mechanical ventilation in the study ICU with a mandatory mode between enrollment and 72 hours after enrollment (excluding time spent in spontaneous modes).
- Time from enrollment to initiation of assigned mode of mechanical ventilation
- Receipt of a "Mode Modification Sheet" completed by treating clinicians

Exploratory Efficacy and Safety Outcomes

- Median exhaled tidal volume (mL/kg predicted body weight (PBW)) on each study day

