10.0 Statistical Considerations

Sample size justification.

The purpose of this trial is to assess feasibility of a cluster-randomized, cluster-crossover design. To assess whether compliance can be maintained after cross-over events, we will need to observe two cross-over events to each mode while maintaining an equal number of treatment blocks for each mode. Doing so will require a total of 9 months. Based on the experience of a prior trial in the same ICU,⁷⁰ we anticipate an average of 75 patients on mechanical ventilation will be enrolled per month. In 9 months, we expect to enroll 675 patients, of whom 69 will be enrolled during washout periods and excluded from the primary analysis. The resulting 606 patients will be included in the primary analysis.

While the sample size was determined to demonstrate feasibility of the cluster-crossover design, we anticipate this pilot will be the largest randomized trial of ventilator modes to date, and as such, we plan to compare ventilator free days to day 28 (primary outcome) between groups. In a prior cluster-randomized cluster-crossover trial in the same ICU,⁷⁰ mechanically ventilated patients experienced a median of 22 VFDs [IQR 0-25 VFDs] and an intra-cluster intra-period correlation of 0.01. With 606 (202 in each group) patients in the primary analysis, a standard deviation in the primary outcome of VFDs of 11 days, and a two-sided alpha of 0.05, the MODE trial will have 80 percent statistical power to detect an absolute difference between groups in the sole primary clinical endpoint of Ventilator Free Days of 3 days.

Primary Analysis of the Primary Clinical Outcome

The sole pre-specified primary outcome of ventilator free days will be compared between the three trial groups in an intention-to-treat fashion among all patients enrolled in the trial except those admitted during one of the 3-day washout periods. To estimate the conditional effect of a group assignment on an individual patient given the values of the covariates for that patient, we will use a proportional odds model with independent covariates of group assignment (volume control, pressure control, or adaptive

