Each of the exploratory outcomes will be compared between groups in an intention-to-treat fashion in the primary analysis population. Continuous outcomes will be compared between groups in a similar manner as the primary clinical outcome. A logistic model will be used for binary outcomes, a multinomial model for categorical outcomes, and a proportional odds model for ordinal and continuous outcomes.

Corrections for multiple testing

We have pre-specified a single primary clinical outcome, which will have a test of statistical significance for difference between groups. Consistent with recommendations of the Food and Drug Administration and the European Medicines Association, the clinical outcome will be tested using a two-sided p-value with a significance level of 0.05. For all other analyses, emphasis will be placed on the estimate of effect size with 95% confidence intervals, as recommended by the International Committee of Medical Journal Editors, and no corrections for multiple comparisons will be performed.

Handling of missing data

The primary outcome is not anticipated to be missing for any patients. Missing data will not be imputed for the primary outcome or any secondary or exploratory outcomes. In adjusted analyses, missing data for covariates will be imputed using multiple imputations.

Interim Analysis

In addition to ongoing monitoring of safety throughout the trial, we will plan for the DSMB to conduct a single interim analysis for safety after the ICU has been assigned to each of the three study modes, that is, after enrollment of patients for 3 months. At the interim analysis, the DSMB will evaluate the incidence of the following outcomes across the study groups (volume control, pressure control, or adaptive pressure control):

- Pneumomediastinum or pneumothorax during the course of mechanical ventilation,
- Episodes of hypoxemia while receiving invasive mechanical ventilation: SpO₂ < 85% for more than 5 minutes,
- In-hospital mortality to study day 28.

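### The only analysis stated for the feasibility outcomes compares the modes with each other; none estimates the level of adherence or whether it holds across crossovers

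*Combined protocol and SAP*

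**What the plan says.** All references are to the combined protocol and SAP.

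- **Aim and hypothesis (3.1, 3.2).** The first aim is "To assess the feasibility of a cluster-randomized, multiple-crossover trial comparing volume control, pressure control, and adaptive pressure control modes". The matching hypothesis is "Comparing volume control, pressure control, and adaptive pressure control ventilation among mechanically ventilated ICU patients will be feasible". No numerical criterion is attached to either.
- **Sample size justification (10.0).** "The purpose of this trial is to assess feasibility of a cluster-randomized, cluster-crossover design". The duration follows from a specific question: "To assess whether compliance can be maintained after cross-over events, we will need to observe two cross-over events to each mode".
- **Outcomes (1.0, 7.6).** There are four feasibility outcomes: exposure, adherence, time to initiation of the assigned mode, and receipt of a Mode Modification Sheet. They are defined as levels, for example "Exposure to assigned study mode in first 3 days: proportion of time in the assigned mode while receiving invasive mechanical ventilation in the study ICU" over the first 72 hours. The trial summary lists them among the exploratory outcomes.
- **Analysis (10.0).** "Each of the exploratory outcomes will be compared between groups in an intention-to-treat fashion in the primary analysis population". Logistic, multinomial or proportional odds models are used according to outcome type, and continuous outcomes are handled much as the primary outcome is. For everything except the primary test, emphasis falls on effect sizes with 95% CIs.
- **Sensitivity analysis (10.0).** The primary and feasibility analyses are repeated with patients from the 3-day washout periods included.
- **Prior experience (7.3).** Monitoring with feedback "successfully achieved 80% compliance with the assigned intervention in a prior cluster-crossover trial of ventilator settings in the same ICU". This is offered as background and is not set as a target.

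**The concern.** The plan asks two questions about feasibility: is adherence to an assigned mode adequate, and is it maintained after the unit switches? The first concerns a level, the second a change over time. The analysis it names answers a third question, whether adherence differs between the three modes. That is worth knowing, but it does not stand in for the other two.

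At stake is the main deliverable of the pilot. Without a planned estimate, the figure to be called the feasibility result, and the way the crossovers are examined, would be chosen after the data are seen. The crossovers that nine months were chosen to supply would have no analysis of their own.

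**Working it through.** **1. The plan's own figures.** 75 patients a month × 9 months = 675; 675 − 69 in washout = 606; 606 / 3 = 202 per mode; 606 / 9 = 67.3 per block. The only power statement concerns ventilator-free days: 3 / (11 × √(2/202)) = 2.74, and Φ(2.74 − 1.96) = 0.783, close to the stated 80%. No precision or power is given for any feasibility outcome.

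**2. What a between-mode contrast can show.** Three illustrative patterns:

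| Pattern | Volume | Pressure | Adaptive | Contrast |
|---|---|---|---|---|
| Uniformly high | 90% | 90% | 90% | difference 0, odds ratio 1 |
| Uniformly low | 30% | 30% | 30% | difference 0, odds ratio 1 |
| Falling 90%, 70%, 50% over the three cycles in every mode | mean 70% | mean 70% | mean 70% | difference 0 |

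The contrast cannot tell these apart, although they mean very different things for a larger trial.

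**3. Whether another stated analysis fills the gap.**
- The washout sensitivity analysis changes the population but keeps the between-mode comparison. It matters here because patients enrolled in the last 3 days of a block are the ones whose 72-hour window can run past a switch, and the primary analysis population leaves them out.
- If the primary model's form carries over to the continuous feasibility outcomes, it brings a spline of calendar day (1 to 272). That term adjusts for season and trend. No estimate from it is planned, and calendar day is not time since a switch.
- No analysis by block, by cycle or by days since the switch is stated.

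**4. Precision of an overall level.** Assumptions: true adherence 80%; binary variance 0.8 × 0.2 = 0.16, the largest possible for a 0-to-1 quantity with that mean; intra-block correlation (ICC) 0, 0.01 or 0.05. The plan gives 0.01 for ventilator-free days and nothing for adherence.

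Half-width = c × √(0.16 × DE / 606), with DE = 1 + (67.3 − 1) × ICC. The multiplier c is 1.96 (z), or 2.306 (t on 8 df, for nine blocks).

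| ICC | DE | z | t, 8 df |
|---|---|---|---|
| 0 | 1 | 3.2 points | not needed |
| 0.01 | 1.66 | 4.1 | 4.8 |
| 0.05 | 4.32 | 6.6 | 7.8 |

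Per mode (n = 202, z): 1.96 × √(0.16 × DE / 202) = 5.5, 7.1 and 11.5 points. A t multiplier would widen the last two. Per block (about 67 patients, sampling error only): 1.96 × √(0.16 / 67) = 9.6 points.

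**5. Precision of a change between cycles.** Pooled over modes, each cycle has three blocks and about 202 patients. Half-width of a difference between two cycles = c × √(2 × 0.16 × DE / 202).
- z: 7.8, 10.1 and 16.2 points at ICC 0, 0.01 and 0.05.
- t on 4 df (nine blocks less 1 for the mean, 2 for mode and 2 for cycle; multiplier 2.776): about 14 points at 0.01 and 23 at 0.05.

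A marked decline such as 90% to 50% would show; a modest one would not. Within one mode there is a single block per cycle, so a change there cannot be separated from ordinary month-to-month variation.

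**The case against.** The strongest reply is that nothing important would be missed. Staff review modes up to four times a day on weekdays and look into why patients are not on the assigned mode (7.3). The DSMB reviews adherence and may recommend stopping for poor performance (13.0). The outcomes are themselves absolute quantities, so per-mode levels will be available from the data and the fitted models. This stands in part. A reader might infer that low adherence would pass unnoticed, or that the trial's data could neither support nor refute feasibility; the documents do not bear out either. But monitoring and oversight are operational. They do not fix in advance which estimate answers the feasibility aim.

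A second reply is that time is already modelled and washout patients are already examined. Both facts stand, so it would be wrong to say that time is absent from the plan. Neither yields a planned estimate of change in adherence.

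Third, differences between modes matter: one unworkable mode would undermine a three-mode trial, and unequal adherence affects separation of the groups. This stands, and is why the comparison should stay. With no criterion stated, no particular pair of adherence levels can be called plainly feasible or infeasible.

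Fourth, a pilot need not have a pass mark. That is fair, and the point does not depend on one.

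**Conclusion.** The concern holds in this form: the plan states feasibility as its purpose and sets its duration by a question about compliance after crossovers, but the one analysis it states for the feasibility outcomes addresses neither the level of adherence nor its change across blocks or after a switch. The mismatch follows from the definition of a contrast and needs no numerical assumption. It should be corrected; it does not compromise the data.

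The precision figures show only that the remedy is workable. They rest on an assumed 80% level and assumed correlations. Binary variance overstates the spread of a per-patient proportion of time, while z with nine blocks understates the uncertainty, so the z-to-t ranges are approximate. The overall level can be estimated usefully; change across cycles only coarsely.

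A reader might take the 80% in section 7.3 as the plan's benchmark. It describes compliance with a different assigned intervention in a prior trial, and the plan does not adopt it.

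**What to change.** In section 10.0, give the feasibility outcomes their own analysis paragraph:

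1. **Main analysis.** Estimate 72-hour exposure and adherence, overall and per mode, with 95% CIs that allow for clustering by block and use a t reference with few degrees of freedom.
2. **Maintenance.** Report adherence for each of the nine blocks. Estimate change across the three cycles pooled over modes, and by days since the switch, with a version that includes washout patients. Present within-mode change as descriptive only.
3. **Secondary.** Keep the between-mode comparison as now written.
4. **Optional.** State in advance the level the investigators would regard as feasible, with reasons. The prior trial's 80% is one possible reference, subject to the difference in intervention.

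The cost is SAP wording and a few extra tables from data already extracted automatically. Enrolment, conduct and clinical care do not change. If a level is named, the investigators commit to it before seeing the results.

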Exploratory Outcomes	Feasibility Outcomes 
 Exposure to assigned study mode in first 3 days: Proportion of time in the assigned mode while receiving invasive mechanical ventilation in the study ICU between enrollment and 72 hours after enrollment

	
 • Adherence to study mode in first 3 days: Proportion of time in the assigned mode while receiving invasive mechanical ventilation in the study ICU with a mandatory mode between enrollment and 72 hours after enrollment (excluding time spent in spontaneous modes) • Time from enrollment to initiation of assigned mode of mechanical ventilation • Receipt of a “Mode Modification Sheet” completed by treating clinicians 
Exploratory Efficacy and Safety Outcomes
 
 • Median exhaled tidal volume (mL/kg predicted body weight) on each study day • Exhaled tidal volumes above target range: Proportion of recorded breaths with exhaled tidal volume values above the target range ($>8\text{mL/kg}$ predicted body weight) on each study day • Hypoxemia during mechanical ventilation: Episodes of hypoxemia during mechanical ventilation: $\text{SpO}_2 < 85\%$ for more than 5 minutes • Severe acidemia during mechanical ventilation: Episodes of severe acidemia during mechanical ventilation: $\text{pH} < 7.1$ on blood gas • Number of blood gas laboratory tests per day while receiving mechanical ventilation • Pneumomediastinum or pneumothorax during course of mechanical ventilation • SOFA score daily on the first 7 study days • Delirium and coma-free days to day 28 
Exploratory Clinical Outcomes:
 
 • ICU-free days to study day 28 • Hospital-free days to study day 28 • In-hospital mortality to study day 28
Analysis	The primary analysis of the primary outcome (ventilator-free days) will be conducted in an intention-to-treat fashion using a proportional odds model with independent covariates of group assignment (volume control, pressure control, or adaptive pressure control) and time since beginning enrollment (in days).
Sample Size	The trial will be conducted for a total of 9 months as this is the duration needed to evaluate the feasibility of the cluster-randomized multiple-crossover design. Based on data from a prior trial in the same ICU, we expect to enroll 675 patients, of whom 69 will be enrolled during washout periods and 606 patients will be included in the primary analysis.

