Enrollment (Day 0): date and time of clinical events (hospital admission, ICU admission, intubation); source of admission to study ICU; age; sex; race; ethnicity; height, weight;⁶⁴ SOFA score;⁶⁵ Glasgow Coma Scale score;⁶⁶ Elixhauser Comorbidity Index;⁶⁷ history of present illness; vital signs (temperature, heart rate, systolic blood pressure, diastolic blood pressure, SpO₂); mechanical ventilator settings (mode, set and exhaled tidal volumes, set and actual respiratory rate, minute ventilation, set and total positive end-expiratory pressure, peak pressure, plateau pressure, inspiratory time, flow pattern, FiO₂); serum laboratory values (white blood cell count, hemoglobin, platelet count, sodium, potassium, bicarbonate, creatinine, bilirubin, alanine aminotransferase, aspartate aminotransferase, lactate, arterial and venous pH, PaCO₂, PaO₂, SaO₂).

Daily On-Study (Days 0-28): Vital signs, ventilator settings, screening for and performance of spontaneous awakening trials and spontaneous breathing trials, and serum laboratory values (as above); Mean daily dose of sedative infusions (propofol, dexmedetomidine, morphine, fentanyl, and midazolam); CAM status; RASS score; Daily completion of each element from ICU Liberation Bundle (A-F); Beginning and end time of Spontaneous Breathing Trials; vasopressor and inotrope infusions (norepinephrine, epinephrine, vasopressin, phenylephrine, dobutamine, angiotensin-2, dopamine); “Mode Modification Sheet” (use, time, reason); Characteristics of treating clinicians (respiratory therapist, attending, pulmonary fellow, registered nurse) providing direct care; Use of therapies for refractory hypoxemia (prone positioning, ECMO, neuromuscular blockade, inhaled pulmonary dilators); SOFA score; ARDS criteria by the Berlin Definition;⁶⁸ Stage II or greater AKI by KDIGO criteria;⁶⁹ cardiac arrest, pneumothorax or pneumomediastinum.

Termination (Days 0-28): Vital status at 28 days; time of liberation from invasive mechanical ventilation; receipt and duration of vasopressors; receipt and duration of renal replacement therapy; tracheostomy; duration of ICU and hospital admission.

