- Exhaled tidal volumes above target range: proportion of recorded breaths with exhaled tidal volume values above the target range ($> 8\text{mL/kg PBW}$) on each study day
- Hypoxemia during mechanical ventilation: episodes of hypoxemia during mechanical ventilation: $\text{SpO}_2 < 85\%$ for more than 5 minutes
- Severe acidemia during mechanical ventilation: Episodes of severe acidemia during mechanical ventilation: $\text{pH} < 7.1$ on blood gas
- Number of blood gas laboratory tests per day while receiving mechanical ventilation
- Pneumomediastinum or pneumothorax during course of mechanical ventilation
- SOFA score daily on the first 7 study days
- Delirium and coma-free days to day 28

Exploratory Clinical Outcomes:

- ICU-free days to study day 28
- Hospital-free days to study day 28
- In-hospital mortality to study day 28

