pressure control) and time. Time (in days) will be treated as a continuous variable with values ranging from 1 (first day of enrollment) to 272 (final day of enrollment) and will be analyzed using restricted cubic splines with multiple knots to allow for non-linearity resulting from seasonality or secular trends. In addition to assessing for an overall group effect within the model, we will estimate the differences between each pair of modes by extracting 95% confidence intervals from the model.

Sensitivity Analyses of the Primary Clinical Outcomes:

We will repeat the primary clinical outcome analysis with adjustment for pre-specified baseline covariates.

We will repeat the analyses of the primary outcome and feasibility outcomes among all patients enrolled in the trial including those initiated on invasive mechanical ventilation in the study ICU during one of the pre-specified 3-day washout periods.

Analysis of Effect Modification for the Primary Outcomes.

We will examine whether pre-specified baseline variables modify the effect of study group on the primary clinical outcome using formal tests of statistical interaction in a proportional odds model. Independent variables will include study group assignment, the potential effect modifier of interest, and the interaction between the two (e.g., study group * history of COPD) and time. Significance will be determined by the P value for the interaction term, with values less than 0.10 considered to suggest a potential interaction and values less than 0.05 considered to confirm an interaction.

We will examine whether the following baseline variables modify the effect of study group on the primary outcome:

- Age (continuous variable);
- Duration of invasive mechanical ventilation prior to enrollment (0 minutes; 1 to 360 minutes; >360 minutes);
- Pre-enrollment fraction of inspired oxygen (FiO₂)(continuous variable);
- SOFA score at enrollment (continuous variable);
- Shock receiving vasopressors (yes, no)
- Indication for intubation (categories are not mutually exclusive)
 - Hypoxemic respiratory failure (yes, no);
 - Hypercarbic respiratory failure (yes, no);
 - Altered mental status or airway protection (yes, no);
- Chronic Obstructive Pulmonary Disease (yes, no);

Analysis of the Exploratory, Feasibility, and Clinical Outcomes

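### Daily SOFA is compared between modes without its enrollment value, which gives up power and lets chance severity differences between monthly blocks into the contrasts

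*Combined protocol and SAP*

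**What the plan says.** Section 7.6 lists "SOFA score daily on the first 7 study days" among the exploratory efficacy and safety outcomes. Section 7.5 includes SOFA in the data set headed "Enrollment (Day 0): date and time of clinical events", and again in the daily on-study data for Days 0 to 28.

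For exploratory outcomes, section 10.0 states "Continuous outcomes will be compared between groups in a similar manner as the primary clinical outcome", and specifies "a proportional odds model for ordinal and continuous outcomes". The primary model, described in section 10.0 and the Trial Summary, contains group assignment and calendar time. Time enters as a restricted cubic spline, and there is no patient-level baseline term.

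The one planned adjusted analysis reads "We will repeat the primary clinical outcome analysis with adjustment for pre-specified baseline covariates". It names only the primary outcome and does not list the covariates. Enrollment SOFA appears by name in section 10.0 only as a possible effect modifier of the primary outcome.

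Non-primary results are to be read from effect estimates and 95% confidence intervals, without multiplicity correction.

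**The concern.** An outcome score that is also measured at the start is usually strongly prognostic for its own later values. Leaving it out costs power. It also leaves any chance difference in starting severity inside the estimated mode effect.

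The design makes this more relevant than in a patient-randomized trial. One ICU receives one mode per month, with three months per mode. The time spline can follow slow drift but not month-to-month changes in case mix. A run of sicker months under one mode would show up in the early-day SOFA contrasts and could be read as organ injury or protection caused by that mode.

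Section 9.4 adds some weight. Organ dysfunction is kept out of adverse event reporting, unless judged related, on the ground that it is collected and analysed systematically. Daily SOFA is the listed outcome that covers several organs.

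**Working it through.** **Inputs.** Section 10.0 gives 75 patients per month for 9 months, 69 in washout, 606 analysed, 202 per mode, two-sided alpha 0.05, and a within-period correlation of 0.01 for ventilator-free days. The arithmetic agrees: 75 × 9 = 675; 675 − 69 = 606; 606/3 = 202; 606/9 = 67.3 per month. The correlation rho between enrollment and later SOFA is not given and is varied from 0.3 to 0.7.

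**1. The plan's own figure.** No power is stated for SOFA. The nearest figure is 80% for 3 ventilator-free days with SD 11. SE = 11 × √(2/202) = 1.09; 3/1.09 = 2.74; Φ(2.74 − 1.96) = 78.3%. This reproduces the stated figure to within 2 points.

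**2. Chance difference in enrollment SOFA between two modes.**
- Independent patients: √(2/202) = 0.0995 SD, 95% range ±0.20 SD.
- With a 0.01 within-period correlation (borrowed from ventilator-free days): design effect 1 + (67.33 − 1) × 0.01 = 1.663; √(2/202 × 1.663) = 0.128 SD, 95% range ±0.25 SD.

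These are for raw means. In a simulation with the spline in the model (linear stand-in, 3,000 trials per setting), the unadjusted contrast had an SE of about 0.13 SD even with independent patients, so 0.10 is if anything low.

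**3. What passes into the unadjusted contrast.** Shift = rho × imbalance. For an imbalance of 1.96 × 0.0995 = 0.195 SD, the shift is 0.059, 0.098 and 0.137 SD at rho 0.3, 0.5 and 0.7.

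**4. Power, linear approximation.** Take a contrast with 80% unadjusted power, so that effect/SE = 1.96 + 0.84 = 2.80. Adjustment divides the SE by 1/√(1 − rho²), so power = Φ(2.80/√(1 − rho²) − 1.96).
- rho 0.3: Φ(2.94 − 1.96) = 83.6%
- rho 0.5: Φ(3.23 − 1.96) = 89.9%
- rho 0.7: Φ(3.92 − 1.96) = 97.5%

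**5. The planned model.** A small simulation of the proportional odds model (two groups of 202, independent patients, 60 runs per rho) gave an unadjusted log odds ratio of about 0.48 with SE 0.176, a ratio of 2.73. With adjustment:

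| rho | Log odds ratio | SE | Ratio | Gain over 2.73 | Linear 1/√(1 − rho²) |
|---|---|---|---|---|---|
| 0.3 | 0.51 | 0.177 | 2.88 | 1.06 | 1.05 |
| 0.5 | 0.57 | 0.178 | 3.20 | 1.17 | 1.15 |
| 0.7 | 0.70 | 0.181 | 3.87 | 1.42 | 1.40 |

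The SE barely moves. The estimate moves away from zero because it becomes conditional on enrollment SOFA. The gain in the ratio, and so in power, agrees with step 4. A separate check at rho 0.3 gave SE 0.175 both ways, with the estimate going from 0.50 to 0.53.

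**6. Bias.** In the step 2 simulation with no mode effect, mean estimates were within 0.004 SD of zero with and without adjustment.

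**The case against.** **The unadjusted analysis is valid.** This stands for bias: estimates centre on zero, and with independent patients the reported interval already allows for chance imbalance. A reader might infer that the plan's SOFA test is invalid, since a 0.01 period correlation in baseline severity gave simulated type I error of 5.3%, 7.3% and 9.1% unadjusted (rho 0.3, 0.5, 0.7) against 5.2%, 5.4% and 5.8% adjusted. The documents do not support that reading. The 0.01 is given for ventilator-free days, not SOFA. The excess comes from unmodelled period clustering, a wider matter than SOFA. Adjustment removes most of it here because the simulation routes all period variation through baseline severity.

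**The intervals would not narrow.** A reader might infer intervals about 5%, 13% and 29% narrower, from √(1 − rho²) = 0.95, 0.87 and 0.71. That is a linear-model result. The plan specifies proportional odds, and step 5 shows no narrowing on the log odds scale. This objection stands in full.

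**Enrollment SOFA may not be purely pre-treatment.** Sections 6.3 and 7.1 start the assigned mode at enrollment, and section 7.5 gives no measurement window. A score built from the whole enrollment day could be partly post-assignment, so one cannot say that mode could not have changed it. The fix has to define the window.

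**SOFA is not unique.** Exhaled tidal volume is also recorded at enrollment and is also an exploratory outcome. The assigned mode may already have shaped it by then, so it is a weaker candidate for adjustment.

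**An adjusted SOFA analysis may be planned elsewhere.** The version log mentions alignment with a Statistical Analysis Plan, and the adjustment covariates are not listed here. The point is therefore limited to the text of this document, which confines the adjusted repeat to the primary outcome.

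**The day count.** Enrollment is Day 0 in section 7.5 and day 1 in the ventilator-free-day definition in section 7.6. The first 7 study days could therefore include the enrollment-day score, but no passage says that they do.

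**Conclusion.** The point holds as a modest improvement to one exploratory outcome. The document contains no analysis of daily SOFA that uses enrollment SOFA, although the score is collected. The cost is lost power, plus chance severity differences between blocks (SE about 0.10 SD, or 0.13 SD under the borrowed correlation) passing into the contrasts at a fraction rho. Power of 80% would become about 84%, 90% or 97.5% at rho 0.3, 0.5 or 0.7.

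These figures rest on an assumed rho, a linear approximation, a hypothetical 80% starting point, and SOFA observed in all 202 patients per mode. Death and discharge will reduce that number on later days. At rho 0.3 the gain is small. The primary conclusion is unaffected, and SOFA is not one of the three interim safety outcomes.

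The estimate would become a conditional odds ratio. That fits section 10.0, which already aims at a conditional effect for an individual patient.

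**What to change.** Add to the exploratory-outcomes paragraph of section 10.0:

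- Daily SOFA is analysed for days after the enrollment day, with enrollment SOFA as a covariate alongside group and the time spline.
- Enrollment SOFA uses values from before, or at, the start of the assigned mode.
- The enrollment-day score is not an outcome day. Reconcile the Day 0 label in section 7.5 with the day 1 label in section 7.6 and state which days make up the 7.

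The cost is small. The score is already extracted, although the extraction may need a narrower time window. Missing baseline scores would need the multiple imputation already planned for covariates in adjusted analyses, and the plan should say that it applies here. The odds ratio must be reported as conditional on enrollment SOFA. The change does not deal with SOFA that is unobserved after death or discharge, which needs its own statement.
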